4.2.2 Physiological Complications

Pulmonary embolism

The Treg cell product contains particulates, namely the Treg cells themselves, some of which may aggregate or clump, and in addition there may be particulates from the authorised container closure system (CellSeal vials). When a cell product is administered by venous infusion, the potential for embolism of cells, aggregates of cells or debris to impede the pulmonary vasculature is a concern. Pulmonary vascular obstructions caused by cell infusion may be widespread and are more likely to affect small end-arteriolar branches or capillaries than larger vessels. Therefore, pulmonary embolism (PE) following cell infusion may not present with classical clinical signs of thromboembolic PE. Depending on its extent, PE may be a life-threatening condition and measures will be taken to avoid its occurrence. For this reason, TR006 will be administered through a standard IV administration set that contains a 200 µm filter plus an additional 40 µm filter to remove visible particulates.

Infusion-related circulatory overload

Fluid infusion may occasionally result in circulatory overload presenting as hydrostatic pulmonary oedema. Critically, the clinical features of fluid overload may be indistinguishable from non-cardiogenic pulmonary oedema, as might occur in a transfusion-related acute lung injury (TRALI)-like reaction. Fluid overload will be avoided by minimising the volume administered (maximum volume of cells will be 10ml) and using a slow rate of infusion over 30 minutes.

Biochemical disturbances

It is possible that immune-mediated lysis of Tregs may occur after infusion but as the cells are autologous this is considered unlikely. Furthermore, the cell dose delivered is negligible compared to the number of cells that must be lysed to cause biochemical disturbances associated with massive tumour lysis, rhabdomyolysis or haemolytic transfusion reactions. Nevertheless, measuring LDH levels pre- and post-Treg infusion may be useful in assessing the fate of Tregs. Patients treated with Treg will be investigated pre- and post-infusion for blood levels of LDH, haemoglobin and tumour lysis markers such as K+, Mg+ and bone profile. The blood pressure and ECG of patients will be closely monitored for hypotension and tachyarrhythmias.

4.2.3 Infectious Diseases

Transmission of infectious diseases through the application of cell products is a potential risk of cell therapy especially in immunosuppressed recipients. The two potential sources of infective contaminants are the consumables used during the manufacturing process or adventitious agents introduced during manufacture. All reagents and equipment used in the manufacturing process will be specified for clinical GMP use or CE-marked. TR006 will be produced using validated Standard Operating Procedures (SOPs) in a licensed GMP facility by fully trained, validated staff dedicated to Treg manufacture. The final cell product will be subject to defined release criteria (see IMPD for details).

4.2.4 Malignancy

Malignant disease after treatment with thymus-derived (Treg) cell product could, in principle, arise either as a consequence of transferring neoplastic cells or as a consequence of transferred cells promoting the growth of spontaneous tumours. Neoplastic cells within the cell product might arise during in vitro culture or after transfer into the recipient. Further, the infused regulatory T population might suppress immune responses against malignant cells. Although no long-term data on this aspect of Treg therapy are available, those that have been published did not report safety concerns of this type. Furthermore, the cell dose that will be infused represents approximately 2% of the patient's endogenous regulatory T cell population suggesting that an impact on malignancy will be small.

4.3 The Immunosuppression Regimen

We do not propose any change to our standard immunosuppression. We will continue to use tacrolimus and mycophenolate mofetil as immunosuppression. This is consistent with current standard of care treatment. This is similar to the policy in the recent study of Tregs in heart transplantation [7].

5 Trial Design

5.1 Description of study design

This is a dose escalation, 3+3, open label, Phase I, single centre-trial investigating the safety and feasibility of two doses of autologous thymus derived regulatory Tregs (TR006) infused into 9 paediatric heart transplant patients.

We will enrol 3 patients at the first low dose of $1-3 \times 10^6$ Tregs/Kg (Cohort 1). The first patient in this cohort will receive the treatment and the safety of the infused cell product will be confirmed before infusing the next patient (with at least a 4-week gap). After safety of the treatment is confirmed for the first patient, the second and third patients of this cohort will receive the same dose of TR006 as and when this is possible. A safety review will be carried out after the third patient is treated to then decide to dose for the next cohort.

If safe, then another 3 patients (Cohort 2) will be treated with the second higher dose of 5-10 x 10^{6} Tregs/Kg. Similarly, the first patient in this cohort will receive the treatment and the safety of the infused cell product will be confirmed before infusing the next patient (with at least a 4-week gap). After safety of the treatment is confirmed for the first patient, the second and third patients of this cohort will receive the same dose of TR006.

A safety review will be performed after the third patient dosed as part of Cohort 2. If safe, a final 3 participants (Cohort 3) will be enrolled into the study to be treated at the highest tolerated dose (using the same dosing/safety review strategy as described for Cohort 1 and Cohort 2).

The study will determine the optimal dose of injected Tregs using a single ascending dose (SAD) design with groups of 3 patients in 3 cohorts (total of 9 patients that could be expanded to 12 in case of dose limiting toxicities). However, if a dose limiting toxicity (DLT) is observed in at least 1/3 in Cohort 1, this will result in expanding the low dose to Cohort 2 instead. A final 3 participants (Cohort 3) will be enrolled at the highest tolerated dose to test further the biological activity subject to there being no further DLTs observed at the low dose if expanded to Cohort 2 i.e. no more than 1/6 DLT or there are no more than 1/3 DLTs observed if Cohort 2 was escalated to the high dose.

If both doses are tolerated, there will be a total of n=9 patients in the study (3 at the low dose and 6 at the high dose or 6 at the low dose and 3 at the high dose). If the higher dose can only be assessed from Cohort 3 and there is 1/3 DLT observed, a further 3 patients will need to be treated at this dose to establish the highest tolerated dose. In this scenario, funding for a further 3 participants will be applied for and the total sample size will be 12 participants.

A DLT will be determined from data collected during the 4-week period post TR006 infusion. Patients with no undue toxicity will be managed and continued on therapy. A DLT will be graded according to the National Cancer Institute's Common Terminology Criteria for Adverse Events (CTCAE) on a 1 to 5 sale as follows [37]:

Grade 1: Mild adverse event Grade 2: Moderate adverse event Grade 3: Severe and undesirable adverse event Grade 4: Life-threatening or disabling adverse event Grade 5: Death.

A DLT is a toxicity considered to be related to TR006. The following events will be considered DLTs:

Occurring in the first 72 hours post infusion:

- CTCAE ≥ grade 2 cytokine release syndrome
- CTCAE ≥ grade 2 injection site reaction
- CTCAE ≥ grade 2 fever and/or rigors
- CTCAE ≥ grade 3 bronchospasm
- CTCAE \geq grade 3 hypoxia

Occurring in the first 4 weeks post TR006 infusion:

• CTCAE \geq grade 3 infection

• Moderate or severe acute rejection (as defined by the International Society for Heart and Lung Transplantation (ISHLT) criteria grade II-III) [38]

- CTCAE \geq grade 3 haematological complication (neutropenia, thrombocytopenia, anaemia).
- Any CTCAE ≥ grade 3 toxicity not clearly related to underlying disease

6 Population

9 paediatric patients on the heart transplant register at GOSH will be recruited to the study.

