2.2 Rationale for dose and regimen selection

As part of Cohort 1, 3 patients will be treated with the first low dose of 1-3 x 10⁶Tregs/kg. If well tolerated, a further 3 patients will be treated with the second higher dose of 5-10 x 10⁶Tregs/kg as part of Cohort 2. If a DLT is observed, this second cohort of 3 will continue to be treated with the low dose. An additional 3 patients will form Cohort 3 and will be enrolled at the highest tolerated dose to test the biological activity of the Tregs. Should enrolment at the high dose only begin from the third cohort i.e. from participant 7 and 1/3 DLT is observed at this dose, further funding will be sought to expand this cohort to 6 and therefore treat a total of 12 participants.

The 2 doses were selected to match what we estimate to be the Minimal Anticipated Biological Effect doses based on the ThRIL and ONE studies [10,11]. This will allow us better to capture the safety of the product and biological activity at the selected dose in a more robust manner and also to provide information on the immunological effects of the Treg product.

In our work leading up to this study, we developed a protocol appropriate for translation of expanded thymic Tregs in our GMP facility at Guy's Hospital [12]. We established that 3 different steps are necessary to obtain the Treg product from the thymus; i) Tissue homogenisation, ii) Treg isolation and iii) Treg expansion.

Thymocytes were obtained from discarded thymi combining enzymatic and non-enzymatic procedures. We processed 12 thymi from children aged between 1 month and 13 years undergoing heart surgery. The medium yield of thymocytes isolated from a paediatric thymus was 0.64×10^9 cells/gr of tissue (range 0.35 - 1.08). Thymocytes obtained during this initial phase have been used for Treg isolation. CD3+CD4+CD8-CD25+ T cells were isolated by depleting CD8+ cells using immunomagnetic beads (CD8 microbeads, Miltenyi Biotec) followed by CD25 enrichment (CD25 microbeads, Miltenyi Biotec). The medium final cell yield was 2.19×10^6 Tregs/gr (range 0.59 - 4.03), indicating that from a single thymus, more than 10^7 Tregs can be isolated. The final Treg product had a high cell purity as the percentage of CD3+CD4+CD8-CD25+CD127low was above 80% (range 72-90.8%).

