This study is a Phase I, single-center clinical trial of treatment with autologous thymus-derived Tregs. The first patient in the Cohort 1 will receive the treatment and we will confirm the safety of the infused cell product following the treatment before infusing the next patient (with at least a 4-week gap). After safety is confirmed for the first patient, the second and third patients will receive the same dose of TR006. A safety review will be done after the third patient to decide the dose for the next cohort (Cohort 2). The same process will be done for the next cohorts (Cohort 2 and Cohort 3).

The first cohort (Cohort 1) of patients (n=3) will be treated with a low dose of $1-3 \times 10^6$ Tregs/Kg. Dose escalation to the higher dose (5-10 x 10^6 Tregs/Kg) will only occur if the lower dose is considered well tolerated. In the event a DLT is observed, this will result in expansion of the lower dose cohort.

Participants will be monitored closely for 6 hours during and immediately after TR006 infusion and then also overnight for admission after the TR006 infusion in case of acute toxicity and to facilitate ease of regular sample collection for safety monitoring.

Following discharge, participants and/or their parents/legal guardians will receive daily phone calls for the first two weeks post TR006 infusion (except on day 14 post-dose) to monitor for any adverse events. Participants will be reviewed in person at days 14 and 28 post Treg infusion for safety assessments including clinical blood tests, ECG and echocardiography and continued adverse event monitoring. Thereafter, participants will be reviewed in person at months 2, 3, 6, 9 and 12 post-dose, with a final safety follow-up visit at 24 months post Treg infusion to monitor for any delayed or chronic complications.

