The diagram below (Figure 1) describes the decision-making process for proceeding with the next dosing cohort based on the DLTs experienced. If a DLT occurs in the Cohort 1, the next cohort of 3 patients will be administered to the same dose. If there is no DLT in Cohort 1, another cohort of 3 patients will be administered to next higher dose. From this study design, the trial will be stopped when 2 patients out of 6 receiving the same dose level experience a DLT. At this point, either a MTD will be identified (green endpoints in diagram) or the trial will be stopped for safety (red endpoints in Figure 1).

Based on this study design, a sample size of between 9 and 12 patients will be needed to identify the maximum tolerated dose. The 3+3 design requires that 6 patients are dosed at the selected dose level, this is often a requirement of adaptive design approaches as well (see Figure 1 below). These 6 patients dosed at the final selected dose level will provide useful information on haematological activity which will be expanded upon with the inclusion of additional patients.

Figure 1: DLT decision-making process

A DLT is defined as grade ≥ 2 CRS, grade ≥ 2 injection site reaction, grade ≥ 2 fever and/or rigors, grade ≥ 3 bronchospasm or grade ≥ 3 hypoxia occurring within the first 72 hours post infusion OR a grade ≥ 3 infection, moderate or severe acute rejection (as defined by the ISHLT criteria grade II-III), grade ≥ 3 haematological complication considered to be related to Treg infusion or any grade ≥ 3 toxicity not clearly related to underlying disease occurring within 4 weeks post TR006 infusion (see Section 5.1 for full definition). [38]

For the purposes of the primary endpoint regarding safety, any DLTs after the TR006 administration will be reported and compared.

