10.4 Criteria for the termination of the trial

The trial will be stopped when 2 patients out of 6 receiving the same dose level (2 cohorts) experience a DLT. At this point, either a MTD will be identified (green endpoints in Figure 1) or the trial will be stopped for safety (red endpoints in Figure 1).

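### Section 5.1 expands the low dose after DLTs in 1/3 or more of Cohort 1; at 2/3 or 3/3 this either cannot help or contradicts the stopping rule in 10.4

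*Protocol*

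**What the plan says.** **Expansion after Cohort 1.** Section 5.1 states that if a DLT "is observed in at least 1/3 in Cohort 1, this will result in expanding the low dose to Cohort 2 instead". Cohort 3 then follows "subject to there being no further DLTs observed at the low dose if expanded to Cohort 2 i.e. no more than 1/6 DLT".

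**The same step elsewhere.** Section 2.1 expands the lower dose after any DLT. Section 2.2 has: "If a DLT is observed, this second cohort of 3 will continue to be treated with the low dose". Section 4 has: "In the event a DLT is observed, this will result in expansion of the lower dose cohort". Section 10.2 has: "If a DLT occurs in the Cohort 1, the next cohort of 3 patients will be administered to the same dose". None of these texts has a separate branch for 2/3 or 3/3 at the low dose.

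**Stopping.** Section 10.4 reads: "The trial will be stopped when 2 patients out of 6 receiving the same dose level (2 cohorts) experience a DLT". Section 10.2 carries the same count without the bracket about two cohorts.

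**High dose.** Here the limit is written down. If the high dose starts only with Cohort 3 and "there is 1/3 DLT observed, a further 3 patients will need to be treated at this dose", the trial grows to 12. If Cohort 2 was already at the high dose, 5.1 allows Cohort 3 with at most 1/3.

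**Who applies the rule.** Section 10.1 bases the DMC's cohort decisions on the 3+3 rules in the trial design section, which is Section 5.

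**The concern.** In a 3+3 design, a dose is expanded after one DLT in three because three more patients can still show that the dose is acceptable. After two or three DLTs they cannot. Section 5.1 sets a floor for expansion but no ceiling, so its wording also covers the outcomes for which expansion has no purpose.

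This is the dose rule of a Phase I trial in children, and Section 10.1 points the DMC to it. If it were followed to the letter after 2/3 or 3/3, up to three more children would receive a dose that had already failed the protocol's own criterion, and their results could not alter the outcome. If the stopping rule is held to take precedence, the DMC has two instructions that disagree at the point where it most needs one.

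**Working it through.** **Inputs.** Cohorts of 3; the low-dose expansion rule and the limit of 1 in 6 (5.1); the stop at 2 of 6 at one dose level (10.2, 10.4); a total of 9 to 12 patients (10.2). The protocol gives no DLT rate, so p = 5%, 10%, 20%, 30% and 40% are assumptions.

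**The plan's own figure.** The completed paths under 5.1 are:
- 0/3 low, then at most 1/3 high, then Cohort 3: 3 + 3 + 3 = 9.
- 1/3 low, then 0/3 low (total 1/6), then 3 at the high dose: 9, or 12 if that high-dose cohort shows 1/3.

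This reproduces 9 to 12.

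**What expansion can achieve.** With x DLTs in Cohort 1 and y in an expanded Cohort 2, the low-dose total is x + y out of 6, with y at least 0.
- x = 1: the total is 1/6 if y = 0, so Cohort 3 is possible.
- x = 2: the smallest total is 2/6.
- x = 3: the smallest total is 3/6.

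All eight (x, y) pairs with x = 2 or 3 exceed 1/6. The chance of going on to Cohort 3 is therefore zero before any further child is infused.

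**How often this would arise.** For independent patients with DLT rate p:
- P(2 or 3 of 3) = 3p²(1−p) + p³. At p = 0.20: 0.096 + 0.008 = 0.104.
- P(at least 1 of 3) = 1 − (1−p)³. At p = 0.20: 1 − 0.512 = 0.488.
- Share of literal expansions that cannot succeed = ratio of the two. At p = 0.20: 0.104/0.488 = 0.213.
- P(high dose reached) = P(0/3) + P(1/3) × P(0/3). At p = 0.20: 0.512 + 0.384 × 0.512 = 0.709.

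| Assumed p | P(2 or 3 of 3) | P(at least 1 of 3) | Share that cannot succeed | P(high dose reached) |
|---|---|---|---|---|
| 5% | 0.007 | 0.143 | 5% | 97% |
| 10% | 0.028 | 0.271 | 10% | 91% |
| 20% | 0.104 | 0.488 | 21% | 71% |
| 30% | 0.216 | 0.657 | 33% | 49% |
| 40% | 0.352 | 0.784 | 45% | 31% |

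The last column is the same with and without the fix, because no path starting at 2/3 or 3/3 reaches the high dose.

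**First-patient check.** The table ignores it. If a DLT in the first patient always halted dosing, the remaining route would be a clean first patient followed by two DLTs, (1−p)p²: 0.9%, 3.2%, 6.3% and 9.6% at p = 10% to 40%.

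**Rough anchors in the protocol.** Section 1.4 reports one serious infusion reaction with fever and rigors among 9 adult liver recipients; Section 5.1 lists "grade 2 fever and/or rigors" or worse within 72 hours as a DLT. That gives 1/9 = 11% (exact 95% CI 0.3% to 48%) and P(2 or 3 of 3) = 25/729 = 3.4%. Over the 21 treated patients in Section 1.1 it gives 1/21 = 5% (CI 0.1% to 24%) and 61/9261 = 0.7%. These are adults given blood-derived cells, some at doses above the low dose here, and only serious events are counted. They do not estimate p.

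**The case against.** A reader might infer that the protocol plainly orders three more infusions after 2/3 or 3/3. The documents do not support that, for four reasons.

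- Section 10.4 can be read as stopping the trial at the second DLT, with its bracket only explaining where the 6 comes from. On that reading, expansion after 2/3 would breach 10.4. This stands, but it turns the fault into a contradiction between two sections and does not remove it.
- Section 10.2 names Figure 1 as the decision diagram, with endpoints where the trial stops for safety. It may contain a stop at 2/3. This stands as a limit on what can be concluded; the wording of 5.1 would then disagree with the figure.
- Sections 2.2, 4 and 10.2 speak of a single DLT, which fits the ordinary one-in-three branch. They lack a limit but do not themselves mention 2/3. Section 5.1 also equates no further DLTs with 1/6, which is true only after exactly one DLT, so the intended rule is fairly clear.
- A safety review follows the third patient (5.1, 10.3), two DLTs in a cohort can prompt an extra DMC meeting (12.1), and the first patient of the next cohort is dosed alone. These lower the practical risk. However, 12.1 allows a meeting and requires no stop, and patients 2 and 3 of a cohort have no stated gap between them.

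The larger probabilities also depend on assumed rates of 30% to 40%; at the rough anchors the situation is uncommon.

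**Conclusion.** The point holds in a limited form. It is certain that the expansion wording in 5.1 covers 2/3 and 3/3, and that after either result the 1/6 condition is out of reach. The rule therefore either directs up to three infusions that cannot change the decision or contradicts 10.4, depending on how 10.4 is read. It is not established that the protocol as a whole lacks a stop at 2/3, nor that the infusions would in fact take place.

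The chance of 2 or 3 DLTs in Cohort 1 is 0.7% to 10% at assumed rates of 5% to 20%, and 22% to 35% at 30% to 40%. This assumes independent patients and no effect of the first-patient check, which would lower it. The case for correction rests on the consequence in a paediatric dose rule and the negligible cost of the change, not on a high probability.

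**What to change.** 1. In 5.1, replace *at least* before 1/3 with *exactly*, and add that the trial stops if 2 or more of the 3 patients in Cohort 1 have a DLT.
2. Align 2.1, 2.2, 4 and 10.2 with this, and Figure 1 if it differs.
3. In 10.4, keep the stop at trial level and state that it applies as soon as the second DLT occurs among up to 6 patients at a dose level, without waiting for two full cohorts.

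The cost is wording in the protocol, carried into the DMC charter where it repeats the rule. After 2/3 or 3/3 the trial would end with Cohort 1 at no more than 3 patients, where the literal text of 5.1 goes on to as many as 6. No path that can still succeed is affected.

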6.1 Inclusion Criteria

- 1. Male or female children aged between 0.5 and 16 (inclusive) years of age at date of consent/assent and date of transplant.
- 2. Written informed consent obtained from a parent/legal guardian.
- 3. Registered on the heart transplant list at date of consent and received a heart transplant on enrolment.
- 4. Receiving a single transplanted organ.
- 5. Willing and able to comply with the study visit schedule.

6.2 Exclusion Criteria

- Active viral infection (with HIV (positive for HIV antibody type 1 or 2), hepatitis B (positive HBSAg), hepatitis C (anti-HCV antibody detection), Human T lymphotropic virus (HTLV antibody I/II detection) and syphilis (Treponema pallidum antibody detection)) at date of admission for transplant (Please refer to Table 2 for more details).
- 2. Age under 0.5 year or over 16 years at date of consent and at date of transplant.
- 3. Multi-organ transplant.
- 4. Highly-sensitised patients at high risk of rejection assessed by HLA antibody measurement (cumulative risk of Mean Fluorescent Intensity (MFI) being >5000 of donor specific antibodies from HLA antibody testing).
- 5. Allergy to any component / excipients used for the manufacture of TR006.
- 6. Previous recipient of any organ transplant.
- 7. History of previous sternotomy surgical procedure for congenital heart defect during which has had previous partial or full thymectomy.
- 8. Confirmed diagnosis of DiGeorge Syndrome with absent thymus.
- 9. Participation in another interventional Clinical Trial of Investigational Medicinal Product during the study or within 28 days prior to date of transplant (at the Chief Investigator's discretion).
- 10. Pregnant and lactating patients (females of childbearing potential* with a positive urine pregnancy test at date of transplant).
- 11. Female patients of childbearing potential* who are not willing to use a highly effective method of contraception** for the duration of the trial (defined as from date of transplant to 12 months

post Treg infusion) to prevent pregnancy, or abstain from heterosexual activity.

*Females of child-bearing potential are females who have experienced menarche and are not surgically sterilised (e.g., hysterectomy, bilateral salpingectomy or bilateral oophorectomy) or post-menopausal. Postmenopausal state is defined as no menses for 12 months without an alternative medical cause. A high follicle stimulating hormone (FSH) level in the postmenopausal range may be used to confirm a postmenopausal state in women not using hormonal contraception or hormonal replacement therapy (HRT). However, in the absence of 12 months of amenorrhea, confirmation with more than one FSH measurement is required.

****** Highly effective methods of contraception are those with a failure rate of < 1% per year when employed consistently and correctly. For example:

- combined (oestrogen and progestogen containing) hormonal contraception associated with inhibition of ovulation oral, intravaginal, transdermal.
- transdermal progestogen-only hormonal contraception associated with inhibition of ovulation oral, injectable, implantable.
- intrauterine device (IUD).
- intrauterine hormone-releasing system (IUS)
- bilateral tubal occlusion
- vasectomised partner, provided that partner is the sole sexual partner of the FOCBP trial participant and that the vasectomised partner has received medical assessment of the surgical success.

Sexual abstinence is considered to be a highly effective method only if defined as refraining from heterosexual activity from the date of transplant until 12 months post Treg infusion. The reliability of this method should be evaluated in relation to the duration of the study and the preferred and usual lifestyle of the participant.

- 12. Male patients who are not willing to use an effective method of contraception (condoms), for the duration of the study (date of transplant to 12 months post Treg infusion), when engaging in sexual activity with a female of childbearing potential.
- 13. Patient is considered by the Chief Investigator, for any reason, to be an unsuitable candidate for the study.

7 Trial Procedures

Please refer to Appendix B for trial Schedule of Events (and to

Table 3, Table 4 and Table 5 for a summary of the clinical procedures performed at the study visits).

Most of the assessments from sections 7.3 - 7.5 below all form part of the routine management of paediatric transplant patients with the exception of the translational research and cardiac biopsy samples being collected.

